1.3.3.1. Study Design of SGNLVA-002

This is an ongoing phase 1b/2, open-label, combination-treatment study and is intended to determine the safety, tolerability, and antitumor activity of LV when used in combination with

pembrolizumab in 1L treatment of subjects with locally advanced and/or metastatic triple-negative breast cancer (LA/mTNBC).

There are 3 treatment schedules in this study: a 2.0 or 2.5 mg/kg q3wk LV plus 200 mg q3wk pembrolizumab schedule, a 1.0–1.25 mg/kg q1wk LV plus 200 mg q3wk pembrolizumab schedule, and a 1.5 mg/kg 2q3wk plus 200 mg q3wk pembrolizumab schedule.

1.3.3.2. Safety in SGNLVA-002

At the time of the data cutoff (26 July 2021), 136 subjects have received LV plus pembrolizumab treatment. Ninety-one subjects have been treated with LV q3wk and 45 subjects with LV q1wk in combination with pembrolizumab.

The most common TEAEs reported in $\geq 20\%$ of subjects receiving LV q3wk plus pembrolizumab or LV q1wk plus pembrolizumab are shown in [Table 5](#).

Table 5: Treatment-emergent adverse events occurring in ≥20% subjects treated with LV q3wk or q1wk + pembrolizumab in Study SGNLVA-002 by preferred term

Preferred Term, ^a n (%)	LV q3wk+ Pembrolizumab (N=91)	LV q1wk + Pembrolizumab (N=45)	Total (N=136)
Nausea	60 (66)	22 (49)	82 (60)
Fatigue	57 (63)	24 (53)	81 (60)
Diarrhoea	45 (49)	18 (40)	63 (46)
Constipation	41 (45)	15 (33)	56 (41)
Alopecia	45 (49)	10 (22)	55 (40)
Decreased appetite	36 (40)	11 (24)	47 (35)
Peripheral sensory neuropathy	37 (41)	7 (16)	44 (32)
Vomiting	27 (30)	9 (20)	36 (26)
Abdominal pain	26 (29)	9 (20)	35 (26)
Arthralgia	27 (30)	8 (18)	35 (26)
Weight decreased	26 (29)	8 (18)	34 (25)
Hypokalaemia	26 (29)	6 (13)	32 (24)
Cough	25 (27)	4 (9)	29 (21)
Pyrexia	22 (24)	7 (16)	29 (21)
Headache	25 (27)	3 (7)	28 (21)
Alanine aminotransferase increased	18 (20)	9 (20)	27 (20)
Aspartate aminotransferase increased	16 (18)	11 (24)	27 (20)
Pruritus	21 (23)	6 (13)	27 (20)

^a MedDRA Version 24.0

Please note: Treatment-emergent adverse events are presented and defined as newly occurring (not present at baseline) or worsening after first dose of investigational product.

The 20% cutoff is based on percentages in the “Total” column.

LV=ladiratuzumab vedotin; MedDRA=Medical Dictionary for Regulatory Activities; q1wk=Days 1, 8, and 15 every 21-day cycle; q3wk=Day 1 every 21-day cycle.

Seventy-one of 91 subjects (78%) treated with LV q3wk plus pembrolizumab and 29 of 45 subjects (64%) treated with LV q1wk plus pembrolizumab experienced National Cancer Institute Common Terminology Criteria for Adverse Events (NCI CTCAE) Grade 3 or higher TEAEs. The most common of these events in all subjects were neutropenia (13%), hypokalemia (12%), fatigue (10%), hyperglycemia, and peripheral sensory neuropathy (9%), (Seagen Inc., data on file).

SAEs were reported in 52 subjects (57%) treated with LV q3wk plus pembrolizumab and of these, 26 subjects (29%) had events assessed by the investigator to be related to either LV or

pembrolizumab. Twenty subjects (44%) treated with LV q1wk plus pembrolizumab reported SAEs and of these, 12 subjects (27%) had events assessed to be related to either LV or pembrolizumab (Seagen Inc., data on file). Out of total subjects in SGNLVA-002, the most common SAEs deemed to be related to either LV or pembrolizumab were abdominal pain (4%), colitis, pyrexia (3% each), acute kidney injury, and diarrhea (2% each).

Please see the LV IB for further details on safety of combination therapy.

1.3.3.3. Preliminary Efficacy Data for SGNLVA-002

As of 07 October 2019, LV q3wk in combination with pembrolizumab achieved a confirmed ORR of 35% ([Han 2020](#)). SD was observed in 32 subjects (48%), see [Table 6](#).

Table 6: Preliminary Efficacy for SGNLVA-002: Objective response rate

	Total (N=66) ^a
Confirmed ORR, % (95% CI)	35% (23.5, 47.6)
CR confirmed, n (%)	2 (3%)
PR confirmed, n (%)	21 (32%)
SD, n (%)	32 (48%)
PD, n (%)	8 (12%)
Not evaluable/not done, n (%)	3 (5%)

^a All subjects whose C1D1 date was at least 3 months before the data extract

CI=confidence interval; CR=complete response; ORR=objective response rate; PD=progressive disease; PR=partial response; SD=stable disease.

Source: San Antonio Breast Cancer Symposium Poster, December 2019 ([Han 2020](#))

1.4. Rationale for Study

LIV-1 expression has been linked with malignant progression to metastasis and is associated with lymph node involvement in breast cancer ([Manning 1994](#)). Based on the activity observed in TNBC (Section 1.2.4), LV may also have activity in other solid tumors expressing LIV-1. In order to identify those indications most likely to be successfully treated with LV, we evaluated multiple internal and external sources of data on LIV-1 expression. LIV-1 expression has been detected in a number of cancer types including breast, prostate, melanoma, ovarian, bladder, small cell lung cancer (SCLC), non-small cell lung cancer (NSCLC), head and neck squamous cell carcinoma (HNSCC), esophageal, and gastric adenocarcinoma. Among the 8 primary indications chosen for this trial, prevalence of LIV-1 expression was as high as 99% (SCLC) and largely above 50%. Prevalence of LIV-1-expressing tumors across cancer subtypes based on RNA is similar to that estimated by protein expression (both IHC and mass spectrometry) ([Manning 1988](#); [Manning 1994](#); [Dressman 2001](#); [Tozlu 2006](#); [Unno 2009](#); [Sussman 2011](#); [Zhu 2014](#); [George 2015](#)); (Seagen Inc., data on file).

Patients with advanced solid tumors generally have poor outcomes. Some advances have been made with the introduction of anti-PD(L)1 therapies; however, there remains a high unmet need in patients who progress on anti-PD(L)1 therapies, or patients who are not eligible for

anti-PD(L)1 therapies. Chemotherapy often remains the chosen treatment option for these patients but is associated with poor responses and often high toxicity. LV, with its targeted delivery of a cytotoxic payload, may have enhanced efficacy and safety.

Additionally, there may be benefit in combining LV with pembrolizumab, an anti-PD-1 mAb (Section 3.2.6). Preclinical studies combining other vedotin-conjugated ADC therapies with anti-PD(L)1 agents reported improved efficacy over either drug individually (Cao 2017; Huang 2022). A preliminary report using protein and gene expression data from SGNLV-001 and SGNLV-002 found LV combined with pembrolizumab in subjects with LA/mTNBC had improved infiltration of immune cells to the tumor microenvironment (TME) (Pusztai 2020).

Preliminary clinical findings from the phase 3 Keynote-006 study suggest that rechallenging with pembrolizumab upon disease progression after previous immune checkpoint inhibitor treatment can provide additional disease control in patients with advanced melanoma (Robert 2019). A recent phase 2 study also demonstrated significant antitumor activity and tolerability of pembrolizumab in combination with ipilimumab in patients with unresectable or metastatic melanoma who experienced progressive disease after anti-PD(L)1 immunotherapy (Olson 2021). Furthermore, results from the recent phase 2 LEAP-004 study of lenvatinib plus pembrolizumab demonstrated clinically meaningful and durable responses in patients with advanced melanoma who had progressive disease following previous treatment with anti-PD(L)1 immunotherapy (Arance 2022).

This study is designed to assess the activity of LV in subjects with advanced solid tumors as a monotherapy (Part A, Part B, Part C Arm 1) and in combination with pembrolizumab (Part C Arm 2 and Arm 3).

2. OBJECTIVES

This study will evaluate the efficacy, safety, and pharmacokinetics (PK) of LV in subjects with solid tumors. Specific objectives and corresponding endpoints for the study are summarized in [Table 7](#).

Table 7: Objectives and corresponding endpoints

Primary Objective	Corresponding Primary Endpoint

 Evaluate antitumor activity of LV as monotherapy (Part A, Part B, and Part C Arm 1 [Cohort 8 only]) and in combination with pembrolizumab (Part C Arm 2 and Arm 3, Cohort 8 only) 	
 Investigator-determined confirmed ORR as measured by RECIST v1.1 for all tumor types For prostate cancer, investigator-determined PSA response by Prostate Cancer Clinical Trials Working Group 3 (PCWG3) criteria in addition to ORR
Secondary Objectives	Corresponding Secondary Endpoints

 Evaluate the safety and tolerability of LV as monotherapy (Part A, Part B, and Part C Arm 1 [Cohort 8 only]) and in combination with pembrolizumab (Part C Arm 2 and Arm 3, Cohort 8 only) Evaluate stability and control of disease Evaluate durability of response in subjects who respond to LV as monotherapy (Part A, Part B, and Part C Arm 1 [Cohort 8 only]) and in combination with pembrolizumab (Part C Arm 2 and Arm 3, Cohort 8 only) Evaluate PFS of subjects treated with LV as monotherapy (Part A, Part B, and Part C Arm 1 [Cohort 8 only]) and in combination with pembrolizumab (Part C Arm 2 and Arm 3, Cohort 8 only) Evaluate survival of subjects treated with LV as monotherapy (Part A, Part B, and Part C Arm 1 [Cohort 8 only]) and in combination with pembrolizumab (Part C Arm 2 and Arm 3, Cohort 8 only) Assess PK of LV (Parts A-C) Assess immunogenicity of LV (Parts A-C) 	
 Type, incidence, severity, seriousness, and relatedness of AEs Investigator-determined DCR as measured by RECIST v1.1 Investigator-determined DOR as measured by RECIST v1.1 for all tumors For prostate cancer, investigator-determined PSA-DOR Investigator-determined PFS as measured by RECIST v1.1 for all tumors For prostate cancer, investigator-determined PSA-PFS OS Selected PK parameters for LV, total antibody, and MMAE Incidence of ATAs to LV
Additional Objectives	Corresponding Additional Endpoints

 Assess biomarkers of biological activity and resistance and predictive biomarkers of response 	
 Relationship between biomarkers in blood and tumor tissue to efficacy, safety, or other biomarker endpoints following treatment with LV monotherapy and in combination with pembrolizumab

3. INVESTIGATIONAL PLAN

3.1. Summary of Study Design

This global, open-label, multicenter trial is designed to assess the activity, safety, and tolerability of LV monotherapy for the treatment of solid tumors.

[figure not shown]
Subjects with the following advanced solid tumors will be enrolled:

- Cohort 1: SCLC (Parts A and B)
- Cohort 2: NSCLC-squamous (Parts A and B)
- Cohort 3: NSCLC-nonsquamous (Parts A and B)
- Cohort 4: HNSCC (Parts A and B)
- Cohort 5: esophageal squamous cell carcinoma (esophageal-squamous) (Parts A and B)
- Cohort 6: gastric and gastroesophageal junction (GEJ) adenocarcinoma (Parts A and B)
- Cohort 7: castration-resistant prostate cancer (CRPC) (Part B only)
- Cohort 8: melanoma (Parts B and C)

The study consists of:

- **Part A** (LV q3wk; Cohorts 1 through 6): LV administered by IV infusion at a dose of 2.5 mg/kg on Day 1 of each 21-day cycle (see Section [5.1](#)).
- **Part B** (LV q1wk; Cohorts 1 through 6 will receive 1.0 mg/kg or Cohorts 1 through 8 will receive 1.25 mg/kg; starting with Protocol Amendment 1): LV administered by IV infusion at a dose of 1.0 mg/kg or 1.25 mg/kg on Day 1, Day 8, and Day 15 of each 21-day cycle (see Section [5.1](#)).
- **Part C** (LV 1.5 mg/kg 2q3wk, LV 1.5 mg/kg 2q3wk plus 200 mg pembrolizumab q3wk, LV 1.25 mg/kg q1wk plus 200 mg pembrolizumab q3wk; Cohort 8 only):
 - **Arm 1:** LV administered by IV infusion at a dose of 1.5 mg/kg on Day 1 and Day 8 but not Day 15 of each 21-day cycle as monotherapy.
 - **Arm 2:** LV administered by IV infusion at a dose of 1.5 mg/kg on Day 1 and Day 8 but not Day 15 of each 21-day cycle in combination with 200 mg pembrolizumab administered by IV infusion on Day 1 of each 21-day cycle.
 - **Arm 3:** LV administered by IV infusion at a dose of 1.25 mg/kg on Day 1, Day 8, and Day 15 of each 21-day cycle in combination with 200 mg pembrolizumab administered by IV infusion on Day 1 of each 21-day cycle.

The study design and cohorts for Parts A, B, and C are depicted in [Figure 2](#) and the study schema is depicted in [Figure 3](#).

Figure 2: Study Design and Cohorts – Parts A, B, and C

a Part A will include Cohorts 1 through 6 only.

b In Part B, Cohorts 1 through 6 will receive 1.0 mg/kg LV or Cohorts 1 through 8 will receive 1.25 mg/kg LV (see Section 5.1). The planned LV q1wk doses are 1.0 mg/kg in an initial cohort, to be escalated to 1.25 mg/kg based on safety assessments (details in Section 3.1).

[figure not shown]
c Includes subjects enrolled prior to and after the safety analysis at a selected LV dose.

d Includes subjects enrolled prior to and after the interim analysis for futility at a selected LV dose and schedule.

e Part C for Cohort 8 will start enrollment upon completion of enrollment for Cohort 8 Part B.

Interim analysis for futility will be performed separately for each cohort of Part A and Part B after approximately 12 efficacy-evaluable subjects of a given cohort have been treated at a specific LV dose and schedule (details in Section 9.3.9).

For Part C, randomization will be stratified according to BRAF mutational status (wild-type vs mutated).

Figure 3: Study Schema Overview

Subjects will be enrolled in Part A until the individual tumor cohorts have 12 subjects or activation of Protocol Amendment 1 at each respective investigative site, whichever comes first. Upon activation of Protocol Amendment 1 at each investigative site, all subsequent subjects enrolled at that site will be in Part B. Subjects in Part A may cross over to Part B with sponsor's approval based on emerging safety and efficacy data.

Part B will assess LV q1wk in the tumor cohorts. The planned dose levels in Part B are shown in [Table 8](#). Initially, approximately 12 subjects across the tumor cohorts will be enrolled and receive LV 1.0 mg/kg q1wk. Based on collective safety data from the initial 12 subjects and from the concurrently ongoing phase 1 study SGNLVA-001 evaluating LV q1wk in breast cancer, subsequent enrollment in Part B will either:

- Continue enrolling up to 12 subjects in each tumor cohort at LV 1.0 mg/kg q1wk for interim analysis for futility, or
- Enroll an additional 12 subjects across the tumor cohorts to receive LV 1.25 mg/kg q1wk (Dose Level +1) for safety analysis. If tolerability is demonstrated, enrollment will continue to 12 subjects in each tumor cohort at LV 1.25 mg/kg q1wk for interim analysis for futility.
- Intrapatient dose escalation to a dose level shown to be safe is permitted with sponsor approval if a subject tolerates study treatment.

Table 8: Planned dose levels for Part B (LV q1wk dosing)

Dose Level	Weekly LV Dose (mg/kg/wk)	Maximum LV Dose in a 21-Day Cycle (mg/kg/cycle)
0	1.0	3.0
+1	1.25	3.75

Interim analysis for futility will be performed separately for each cohort after approximately 12 efficacy-evaluable subjects of a given cohort have been treated at a specific LV dose and schedule (Section 9.3.9). Cohorts that successfully pass the interim analysis for futility may, at the sponsor's decision, continue to enroll up to an additional 18 subjects, totaling up to 30 subjects for each tumor cohort at a specific dose and schedule.

Part C will assess LV as monotherapy and in combination with pembrolizumab in subjects with melanoma (Cohort 8). Enrollment in Part C will begin after Cohort 8 Part B enrollment has been completed. Subjects will be randomized to 1 of 3 arms with 30 subjects per arm. The randomization ratio will be 2:1:1 until Arm 1 reaches 30 subjects. Thus, of the first 60 subjects, 30 subjects will be enrolled in Arm 1, 15 subjects will be enrolled in Arm 2 and 15 subjects will be enrolled in Arm 3. This will ensure that Arm 1 reaches the target enrollment sooner. Afterwards, the remaining subjects will be randomized in a 1:1 ratio to either Arm 2 or Arm 3. Randomization will be stratified according to B-Raf proto-oncogene serine/threonine kinase gene (BRAF) mutational status (wild-type versus mutated).

- Arm 1 (LV monotherapy 2q3wk): subjects will receive 1.5 mg/kg LV on Day 1 and Day 8 but not Day 15 of each 21-day cycle.
- Arm 2 (LV 2q3wk+pembrolizumab q3wk): subjects will receive 1.5 mg/kg LV on Day 1 and Day 8 but not Day 15 of each 21-day cycle and 200 mg pembrolizumab on Day 1 of each 21-day cycle.
- Arm 3 (LV q1wk+pembrolizumab q3wk): subjects will receive 1.25 mg/kg LV on Day 1, Day 8, and Day 15 of each 21-day cycle and 200 mg pembrolizumab on Day 1 of each 21-day cycle.

Pembrolizumab administration will be capped at 35 cycles (approximately 2 years).

Disease progression for determining eligibility of treatment continuation will be based on immune Response Evaluation Criteria in Solid Tumors Version 1.1 (iRECIST) for subjects in Part C (Arms 2 and 3) (Appendix I).

Additional tumor types may be included in this study in future protocol amendments. Alternative dosing regimens, biopsy/biomarkers, and LV-based combinations may be tested in future amendments.

For non-prostate cancer subjects, tumor assessment according to Response Evaluation Criteria in Solid Tumors version 1.1 (RECIST v1.1) (Appendix H) will be performed every 6 weeks (± 3 days) for the first 12 months after the first dose of LV and then every 12 weeks (± 7 days) thereafter. Objective responses (complete response [CR] or partial response [PR]) will be confirmed with repeat scans 4–6 weeks after the first documentation of response.

For prostate cancer subjects (Part B, Cohort 7), prostate-specific antigen (PSA) will be assessed every 3 weeks (± 3 days). Soft tissue tumor assessment by computed tomography (CT) or

magnetic resonance imaging (MRI) and bone scans according to the Prostate Cancer Clinical Trials Working Group 3 (PCWG3) criteria will be assessed every 8 weeks (± 7 days) for the first 24 weeks, then every 12 weeks (± 7 days) thereafter.

Safety will be assessed throughout the study, and AE severity will be graded using the NCI CTCAE, version 5.

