9.3.9. Interim Analyses

Interim analysis for futility will be performed separately for each cohort in Part A and Part B after approximately 12 subjects of a given cohort have been treated with a specific LV dose and schedule (LV q3wk at 2.5 mg/kg, LV q1wk at 1.0 mg/kg, or LV q1wk at 1.25 mg/kg [Section 3.1]) and are efficacy evaluable post-baseline. Enrollment to each cohort may be held after approximately 12 subjects for interim futility analysis of the respective cohorts.

The Bayesian predictive probability of success (PPoS) approach will be used to determine the futility criteria (Lee 2008). At the time of each interim analysis, the PPoS will be calculated. PPoS is the probability of achieving “success” should the cohort be continued to the maximum sample size of 30 given the data observed at interim, and a cohort is considered “success” if the posterior probability that the ORR exceeds the response rate of current standard of care (i.e., 15% for SCLC, 10% for NSCLC-squamous, 15% for NSCLC-nonsquamous, 10% for HNSCC, 10% for esophageal-squamous, 15% for gastric and GEJ adenocarcinoma, 10% for melanoma, and 30% for CRPC as referenced in Section 3.1) is greater than 90%.

The ORR observed at interim will be counted as a response for the calculation of PPoS. Table 20 summarizes the PPoS based on the number of responses observed among the first 12 subjects.

Table 20: PPoS based on response among the first 12 subjects

No. of responses ^a among the first 12 subjects	Predictive Probability of Success							
	SCLC (p ₀ =15%)	NSCLC-squamous (p ₀ =10%)	NSCLC-nonsquamous (p ₀ =15%)	HNSCC (p ₀ =10%)	Esophageal-squamous (p ₀ =10%)	Gastric or GEJ adenocarcinoma (p ₀ =15%)	Melanoma (p ₀ =10%)	CRPC (p ₀ =30%)
0	0.05%	0.2%	0.05%	0.2%	0.2%	0.05%	0.2%	0.0007%
1	2%	8%	2%	8%	8%	2%	8%	0.05%
2	16%	36%	16%	36%	36%	16%	36%	0.8%
3	45%	73%	45%	73%	73%	45%	73%	6%
4	77%	94%	77%	94%	94%	77%	94%	21%
5	94%	100%	94%	100%	100%	94%	100%	48%

p₀ is the response rate of current standard of care of each cohort

a Including both confirmed and unconfirmed CR or PR observed at interim

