1 INTRODUCTION

This document outlines the statistical methods to be implemented within the scope of Protocol SGNLVA-005, entitled “Open-Label Phase 2 Study of Ladiratuzumab Vedotin (LV) for Unresectable Locally Advanced or Metastatic Solid Tumors”, Original version dated 22Apr2019. Results of the proposed analyses will become the basis of the clinical study report for this protocol.

The purpose of this plan is to provide specific guidelines from which the analysis will proceed. All planned analyses specified in this document will be performed. Any changes to this plan, in the form of “post hoc” or “data driven” analyses will be identified as such in the final clinical study report (CSR). Any changes will either be reflected in amendments to this plan before the database lock or specifically documented in the CSR.

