5.4.2 Best Response

The determination of antitumor activity will be based on objective response assessments made by the investigator according to the RECIST v1.1 (Eisenhauer 2009). Only response assessments on or prior to start date of any new anticancer therapy will be considered for best response. The patient's best response will be the best demonstrated response to date that has been confirmed, when confirmation is required (i.e. for PR and CR only). The patient's best response will be used in determining the ORR.

A response (CR or PR) will be considered confirmed if the subsequent disease assessment conducted no earlier than 4 weeks after the initial response still shows CR or PR. A patient will have a best response of SD if there is at least one SD assessment (or better) ≥ 5 weeks after the start of treatment and the patient does not qualify for confirmed CR or PR. RECIST v1.1 outlines scenarios for best overall responses when confirmation of CR and PR is required.

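### Crossover and dose escalation do not end the response window, so a response first seen after a switch can count toward the starting LV regimen's ORR, DOR and PFS

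*Protocol*

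**What the plan says.** Protocol section 3.1 permits two changes of LV regimen on study. The first is that "Subjects in Part A may cross over to Part B", with the sponsor's approval and in light of emerging safety and efficacy results, that is, from 2.5 mg/kg every 3 weeks to weekly dosing. The second is within Part B: "Intrapatient dose escalation to a dose level shown to be safe is permitted with sponsor approval", provided the subject tolerates treatment. Neither sentence carries an analysis rule.

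SAP section 5.4.2 defines the outcome behind ORR: "The patient's best response will be the best demonstrated response to date that has been confirmed". It sets one limit on the window: "Only response assessments on or prior to start date of any new anticancer therapy will be considered for best response". The DOR rules (Protocol 9.2.4, SAP 6.5.2.2) censor at new anticancer treatment, at removal from study, or at the last assessment of a subject without progression. PFS (Protocol 9.2.5, SAP 6.5.2.3) takes over the same rules. None of them mentions a change of LV dose or schedule.

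The estimates are meant to be specific to a regimen. Under Protocol 9.3.9 the futility analysis takes place after about 12 subjects "of a given cohort have been treated with a specific LV dose and schedule", and PPoS projects the cohort to "the maximum sample size of 30 given the data observed at interim". The footnote to Table 20 counts unconfirmed as well as confirmed responses at the interim.

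The SAP is written to the protocol's "Original version dated 22Apr2019". Its section 3 has every subject on 2.5 mg/kg every 3 weeks. Part B was added by Amendment 01, so the SAP does not consider a switch.

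**The concern.** A subject moved from one LV regimen to another is still on LV. On an ordinary reading no new anticancer therapy has begun, so the window stays open. By-cohort analysis on the full analysis set then places whatever is seen next in the cohort where the subject sits. If that is the cohort of entry, the ORR for a dose and schedule includes responses obtained on a different one. In the same way, DOR and PFS time after the switch is attributed to the starting regimen.

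The distinction matters because the regimens may differ in activity. In the phase 1 breast cancer data (Protocol Table 4), partial responses were 0 of 10 at 1.0 mg/kg weekly and 8 of 29 (28%) at 1.25 mg/kg weekly. Those groups are small and in another tumour, but they show the contrast that would be blurred if responses after escalation were reported under 1.0 mg/kg. The interim reading is also sensitive, because the futility line for Cohorts 1 to 6 lies between one and two responses.

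**Working it through.** **Inputs.** Interim n = 12, maximum N = 30, success if the posterior probability that ORR exceeds p0 is above 90%, futility line PPoS < 10% (Protocol 9.3.9). For Cohorts 1 to 6, p0 is 10% or 15%. Cohorts 7 and 8 have no Part A and are planned in Part B only at 1.25 mg/kg, the higher level in Protocol Table 8, so neither switch applies to them. The prior is not stated. I assume a Beta prior of weight 1 with mean p0 + 0.10, that is Beta(0.20, 0.80) for p0 = 10% and Beta(0.25, 0.75) for p0 = 15%.

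**Step 1: reproduce Table 20.** Let r be the smallest number of responses in 30 that meets the success criterion. Then PPoS(x) = Σ BetaBinomial(y; 18, a + x, b + 12 − x) over all y with x + y ≥ r. This gives r = 6 for p0 = 10% and r = 8 for p0 = 15%.

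| Responses in 12 | p0=10%: computed | Table 20 | p0=15%: computed | Table 20 |
|---|---|---|---|---|
| 0 | 0.25% | 0.2% | 0.06% | 0.05% |
| 1 | 8.3% | 8% | 2.5% | 2% |
| 2 | 36.4% | 36% | 15.9% | 16% |
| 3 | 73.2% | 73% | 45.5% | 45% |
| 4 | 94.4% | 94% | 77.2% | 77% |
| 5 | 99.6% | 100% | 94.5% | 94% |

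Every cell agrees within 0.6 point. Moving the prior mean between p0 + 0.05 and p0 + 0.20 gives 7.7–9.5% at 1/12 and 35.2–38.7% at 2/12 for p0 = 10%. For p0 = 15% it gives 2.3–3.0% and 15.2–17.4%. The position of the line is therefore stable over that range. A flat Beta(1, 1) prior gives 28% at 1/12 for p0 = 10% and does not reproduce the table.

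**Step 2: effect of one response after a switch.** Take a cohort with one response on the starting regimen and one first seen after a switch.
- ORR with both counted: 2/12 = 16.7% (90% exact CI 3.0–43.8%).
- ORR with only the first counted: 1/12 = 8.3% (0.4–33.9%).
- Difference: 1/12 = 8.3 points.
- PPoS: 36% against 8% (p0 = 10%), or 16% against 2% (p0 = 15%).

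**Step 3: how likely that is.** The documents give neither the number of switchers nor their later response rate, so these are assumptions. With exactly one response on the starting regimen, the chance that at least one of k switchers adds another is 1 − (1 − q)^k, where q is the response rate after the switch.

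| k of 12 | q=5% | q=10% | q=20% | q=30% |
|---|---|---|---|---|
| 1 | 5% | 10% | 20% | 30% |
| 3 | 14% | 27% | 49% | 66% |
| 6 | 26% | 47% | 74% | 88% |

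**Step 4: what depends on the interim.** Part A has 6 cohorts × 12 = 72 subjects, its full allocation in Protocol 9.1, so a favourable Part A reading opens no further Part A places. Part B's 252 equals 12 + 8 × 30. That fits about 12 subjects in total at 1.0 mg/kg, with expansion at 1.25 mg/kg. Enrolling 12 per cohort at 1.0 mg/kg is the alternative branch in Protocol 3.1.

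**The case against.** The strongest objection is that SAP 5.4.2 assigns nothing to a regimen. It sets a window for each subject and was written when only one regimen existed. A reader might infer that the plan expressly credits the starting regimen. The documents do not say so; that result follows only if subjects stay in their cohort of entry. The protocol's reference to treatment at a specific dose and schedule could also be read as crediting the new regimen, or neither. This stands as a limit on the wording, but it does not remove the problem. Counting crossed-over subjects in Part B would add selected, already treated subjects to cohorts where passing the interim may open up to 18 more places.

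A reader might also infer that a failing cohort would be kept enrolling. The documents do not support that for the starting regimens. Part A is capped, a 12-per-cohort interim at 1.0 mg/kg arises only if enrolment stays at that dose, and subjects at 1.25 mg/kg have no higher Part B level. Stopping is also at the sponsor's discretion.

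Protocol 3.1.1 bars retreatment after progression, so switchers would mainly be subjects with stable disease or an unconfirmed response. A later response may then owe something to the starting regimen. Nor do the documents show that switching is driven by an individual's lack of response: crossover rests on emerging safety and efficacy data, and escalation on tolerability. Both points reduce the likely size of the effect, but neither supplies an attribution rule.

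Finally, counting all responses regardless of permitted switches is a legitimate estimand. It needs to be chosen and labelled, and at present it would arise by default.

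**Conclusion.** The point holds as a gap that biases regimen-specific estimates. Applied as written, and with analysis by cohort of entry, the rules count a response first seen after crossover or escalation toward the starting dose and schedule. They also run DOR and PFS through the switch. The firmest effect is on the reported ORR, at 8.3 points per such response in 12, together with DOR and PFS.

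The PPoS movement (8% to 36%, or 2% to 16%) can be read from Table 20 without knowing the prior. It is a conditional case: exactly one response on the starting regimen and one after a switch. It changes the reported PPoS more than it changes enrolment. The total effect cannot be sized, because the documents do not give the number of switchers or their response rate; the range in step 3 rests on assumed values.

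**What to change.** Update the SAP to the current protocol, which Protocol 9.3 allows up to database lock, and add the following:

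1. Define the analysis cohort by tumour type and starting LV dose and schedule. Do not add crossed-over subjects to Part B denominators.
2. For the primary ORR and for PPoS, count only responses first documented before the first dose of a different LV schedule or a higher dose level. Allow confirmation after the switch. Closing the window outright at that dose would be too strict: confirmation comes 4 to 6 weeks after first documentation, so a genuine response on the starting regimen could be lost.
3. List responses first seen after a switch separately, by old and new regimen, and give an all-responses ORR as a sensitivity analysis.
4. Add a sensitivity analysis of DOR and PFS censored at the switch. Keep it as a sensitivity analysis, because a switch that depends on tolerability or emerging data may be informative censoring.
5. State the prior used for PPoS, so that the interim can be recomputed under either counting rule.

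The cost is SAP wording, one listing and a few extra runs. Dose and assessment dates are already collected, and no dosing or crossover rule changes. The starting regimens' ORR may come out slightly lower.
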